Power. This trial is powered to detect a between arm difference (AO vs. A+P) in the change of MVPA (0-6 mos.) of 10 min./d. This represents an additional 70 min. of MVPA/wk. An increase in MVPA of this magnitude is associated with improved adiposity and cardiovascular fitness in typically developing adolescents^{56, 57}, and potentially in adolescents with IDD, a group with low baseline levels of MVPA^{58, 59}. Statistical power to detect a significant effect on MVPA across 6 mos., the primary aim in the proposed 2-arm randomized design, depends on the following parameters: the number of participants in each arm (J), the number of measurements ($n = 21$; 7 days at 0, 3, and 6 mos.), correlations among repeated measures (r), and effect size (f). Assuming a conservatively large standard deviation for change in MVPA in both arms (35 min./d), corresponds to a small to moderate effect size ($f = 0.14$). The correlation between repeated measures of MVPA (3 mo. interval) in our pilot trial was $r = 0.22$. To be conservative, we assumed a higher correlation ($r = 0.25$) for this sample size calculation. Based on these assumptions, power analysis using G*Power 3.1.9.2 shows a sample of 114 adolescents ($J = 57/\text{arm}$) would provide 81% power to test overall between arm differences across time, i.e., group effect. This sample size would also provide $\geq 80\%$ power to detect a group difference in change, i.e., time-by-group interaction, as small as $f = 0.09$. Missing data will be fully recovered via multiple imputation as discussed subsequently, which will remove or minimize (if present) confounding effects of missingness on our statistical power. The secondary aims were not powered to detect between group differences.

Baseline equivalence. We will compare baseline characteristics, e.g., age, sex, race/ethnicity, BMI, IDD diagnosis, etc., between the AO and A+P arms using independent-samples *t*-test for continuous variables and chi-square/Fisher test for categorical variables, to assess the degree to which randomization resulted in equivalent groups. Variables that demonstrate a significant nonequivalence will be controlled for in our analytic models to improve the accuracy in estimates of the intervention effect. Prior to modeling, missing data for each outcome will be imputed as described subsequently.

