Primary aim analysis. Our primary aim, to compare changes in MVPA (min./d) between the AO and A+P arms from 0 to 6 mos., will be evaluated using general mixed modeling for repeated measures. Specifically, the model will examine linear/nonlinear change over time (21 measurements = 7 days at each of 0, 3, and 6 mos.); i.e., time effect, overall group difference across time, i.e., group effect, and group difference in change, i.e., time-by-group interaction, controlling for day of the week (weekday/weekend) and baseline characteristics imbalanced between the groups. For example, a significant interaction will indicate that adolescents in the A+P arm achieve more minutes of MVPA compared to adolescent in the AO arm, and this difference becomes greater across time. A proper error covariance structure will be determined based on relative model fit, e.g., Akaike information criteria, adjusted Bayesian information criteria.

Secondary Aim analysis. Our secondary aim, to compare changes between the AO and A+P arms on the following variables across 18 mos.: 1) MVPA (min./d) and sedentary time (adolescents and parents), 2) cardiovascular fitness, 3) muscular strength, 4) motor ability, and 5) quality of life, will be evaluated using a similar general mixed modeling approach. The models will examine linear/nonlinear change over time (7 days at each of 0, 3, 6, 9, 12, 15, and 18 mos. for MVPA and sedentary time; 0, 6, 12, and 18 mos. for all other outcomes), overall group difference across time, and group difference in change. We will also longitudinally compare the percentage of adolescents achieving the 60 min./d MVPA (US recommendation) using generalized mixed modeling for repeated binary measures (yes/no in each observed day). In a secondary analysis, we will fit a general mixed model that includes cardiovascular fitness, muscular strength, motor ability, and quality of life as time-varying covariates, and assess their association with MVPA aggregated across months controlling for group.

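### The primary model treats baseline MVPA as an outcome with a separate mean per arm, so the 0-6 month change contrast is valid but less precise than the collected data allow

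*Combined protocol and SAP*

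**What the plan says.** Analysis plan and statistical power, Primary aim analysis: in the mixed model "the model will examine linear/nonlinear change over time (21 measurements = 7 days at each of 0, 3, and 6 mos". The arm terms are an overall group effect and a time-by-group interaction, and the plan describes the interaction as the between-arm difference in change. The covariates are weekday/weekend and any baseline characteristics found to be imbalanced. No common baseline mean is imposed, and baseline MVPA is not named as a covariate. Under Baseline equivalence, a variable enters the models only if the arms differ significantly on it; the examples are demographic and diagnostic, and the list is open-ended.

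Under Power, the trial is "powered to detect a between arm difference (AO vs. A+P) in the change of MVPA (0-6 mos.) of 10 min./d". The SD is introduced by "Assuming a conservatively large standard deviation for change in MVPA in both arms (35 min./d", which "corresponds to a small to moderate effect size ($f = 0.14". The calculation uses "the number of measurements ($n = 21$; 7 days at 0, 3, and 6 mos". On correlation: "The correlation between repeated measures of MVPA (3 mo. interval) in our pilot trial was $r = 0.22", and "we assumed a higher correlation ($r = 0.25$) for this sample size calculation". The resulting 81% power is stated for the group effect. Neither paragraph says whether the group effect or the interaction is the primary test.

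**The concern.** Randomisation makes the two arms' expected baseline means equal. A model that estimates them separately does not use that fact. With complete (imputed) data, the 0-6 month interaction contrast is then essentially the difference between arms in mean change, with the noise of the baseline week subtracted at full weight. The lower the correlation between baseline and follow-up, the more this costs, and the only pilot correlation that the plan reports is low.

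The other listed test has a different weakness. The group effect averages all three waves, including month 0, when the expected difference is zero, so it dilutes any real effect.

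At stake are precision on the primary aim, in a trial whose sample size has no allowance for dropout, and a primary result that could be read from either of two different tests.

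**Working it through.** **Inputs.** From Power: difference 10 min/d, SD 35 min/d, 57 per arm, 21 measurements, design r = 0.25, pilot r = 0.22 over 3 months. Assumption: two-sided alpha of 0.05, which is not stated but reproduces the plan's power. Powers use the t distribution with 112 df unless noted.

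**1. The plan's own figure.** f = (10/35)/2 = 0.1429. Noncentrality = 114 × 0.1429² × 21/(1 + 20 × 0.25) = 8.14. Power on F(1,112) = 80.8% (79.2% with f rounded to 0.14). The stated 81% is reproduced. It is power for the group effect, and in it 35 acts as the SD of a single day's value.

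**2. What the group effect can detect.** Variance of a 21-day mean = 35² × (1 + 20 × 0.25)/21 = 350, so SD = 18.7 and SE = 18.7 × √(2/57) = 3.50. The 80.8% needs a 10 min/d gap at all three waves, month 0 included.
- True differences of 0, 10, 10 at months 0, 3, 6 average 6.7: power about 47% (48% by normal approximation).
- True differences of 0, 5, 10 average 5: power about 29% (30% by normal approximation).

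**3. Variance of the 6-month contrast.** Let s² be the variance of a week mean, equal across waves, and rho the correlation of baseline and 6-month week means.
- Separate baseline means: 2s²(1 - rho).
- Common baseline mean or baseline covariate: s²(1 - rho²).
- Ratio (1 + rho)/2, so the cut is (1 - rho)/2.

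**4. Values of rho (assumed; none is given).**
- If r = 0.25 holds between all single days, rho = 7 × 0.25/(1 + 6 × 0.25) = 0.70. Ratio 0.85, cut 15%.
- If the pilot 0.22 is a week-mean correlation that also holds over 6 months, rho = 0.22. Ratio 0.61, cut 39%.
- A value between, rho = 0.50: ratio 0.75, cut 25%.

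Fitting time as linear does not remove the loss: under compound symmetry the cut is 16% at rho = 0.70 and 45% at rho = 0.22.

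**5. Power for 10 min/d, 57 per arm.**

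| Reading of 35 | rho | SE, separate | SE, common | Power, separate | Power, common |
|---|---|---|---|---|---|
| Daily SD, r = 0.25 throughout | 0.70 | 3.03 | 2.80 | 90% | 94% |
| SD of change, as worded | 0.70 | 6.56 | 6.04 | 33% | 37% |
| SD of change, as worded | 0.22 | 6.56 | 5.12 | 33% | 49% |

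First row: week-mean variance = 35² × 2.5/7 = 437.5; SD of change = √(2 × 437.5 × 0.30) = 16.2; adjusted SD = √(437.5 × 0.51) = 14.9. Other rows: adjusted SD = 35 × √((1 + rho)/2), which is 32.3 or 27.3.

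**6. Chance baseline gaps.** With no true effect and an observed baseline gap g (A+P minus AO), the expected change contrast is -(1 - rho)g: 30% of the gap at rho = 0.70, 78% at rho = 0.22. For scale, with week-mean SD 20.9 a 1-SE gap is 20.9 × √(2/57) = 3.9 min/d, of which 0.30 × 3.9 = 1.2 min/d returns at rho = 0.70. Over all randomisations, simulated type I error (200,000 draws) is 5.0% at both values of rho. Given a 1-SE gap, rejection is 4-5%; given a gap of 1.96 SE, it is 10% (rho 0.70) to 17% (rho 0.22).

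**The case against.** This is a standard, valid longitudinal model, and the loss may be small: under the inputs that reproduce 81%, the gain is about 4 points of power. That stands, and it limits the point to efficiency and clarity.

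Several stronger readings are tempting, and the documents do not support them.
- A reader might infer that the primary test is an unadjusted change score. The plan leaves the primary test open between two terms, and the group effect is not a change score. The model also controls for day of week and for imbalanced characteristics, and the open-ended list could admit baseline MVPA. That route depends on a significance test, and it is awkward when baseline is already a response.
- A reader might infer that chance baseline gaps produce false effects. Step 6 shows imprecision conditional on the observed gap, with no bias or alpha inflation over randomisations.
- A reader might take 0.22 as the baseline-to-6-month correlation. It is a 3-month figure, and the plan does not say whether it is between days or week means.
- A reader might blame separate baselines for the 33% power. That figure comes from taking 35 literally as the SD of change, which is a separate question.

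Two technical objections also have force. The plan allows nonlinear time and a covariance chosen by fit; if variances differ between waves, a linear-time interaction is not exactly the raw difference in change. And a common baseline mean is justified only if the baseline week is finished before allocation is known. The protocol hands out accelerometers at the baseline visit, and distributes equipment and outlines study requirements after it, but does not time randomisation against the wear week. This second point affects any use of baseline, including the planned change contrast.

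**Conclusion.** The concern holds as a matter of precision and specification. The interaction that answers the stated aim is essentially a change contrast not adjusted for baseline MVPA. It is valid, but its variance is higher than it need be by a fraction that the documents do not fix: a common baseline would remove (1 - rho)/2 of it, about 15% at rho = 0.70 and about 39% at rho = 0.22. Both ends are assumptions about what the plan's correlations measure, and both take equal variances across waves and complete data. For any rho below 1 the direction is the same; only the size is uncertain.

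The group effect is not a better choice. Its 81% assumes a difference that is already present at baseline. Because the plan does not say which test is primary, the choice should be fixed along with the baseline handling.

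**What to change.** In Primary aim analysis:
- Name the month-6 between-arm difference in MVPA as the single primary contrast.
- Treat wave as categorical (0, 3, 6 months) with one common baseline mean: no group term at month 0, group-by-wave terms at months 3 and 6. Equivalently, model only the 3- and 6-month days, with each adolescent's baseline 7-day mean MVPA as a covariate whether or not the arms look imbalanced.
- Use the same form for the continuous secondary outcomes.

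In Power, state whether 35 min/d is a daily SD or the SD of change and whether r is between days or week means, then restate power for the named contrast.

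The cost is SAP wording only, with no new data or participants. One condition applies: the protocol should confirm that the baseline accelerometer week is completed before allocation is known. If it is not, the equal-baseline assumption does not hold.

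### The primary aim is a 0–6 month difference in change, but the plan offers a group effect and a time-by-group interaction without saying which decides, and it misreads what a significant interaction shows

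*Combined protocol and SAP*

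**What the plan says.** All references are to the section on analysis plan and statistical power in the combined protocol and SAP.

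- **Aim.** The Primary aim analysis paragraph sets out "to compare changes in MVPA (min./d) between the AO and A+P arms from 0 to 6 mos". The primary aim near the start of the protocol is worded the same way and expects the larger increase in A+P.
- **Model.** It is a mixed model in which "the model will examine linear/nonlinear change over time (21 measurements = 7 days at each of 0, 3, and 6 mos". The same sentence lists a time effect, then "overall group difference across time, i.e., group effect, and group difference in change, i.e., time-by-group interaction".
- **Interpretation.** The paragraph offers one example: "a significant interaction will indicate that adolescents in the A+P arm achieve more minutes of MVPA compared to adolescent in the AO arm", and the sentence ends "and this difference becomes greater across time".
- **Power.** The Power paragraph targets a 10 min/d between-arm difference in change. It then says that 114 adolescents "would provide 81% power to test overall between arm differences across time, i.e., group effect", and separately claims at least 80% "power to detect a group difference in change, i.e., time-by-group interaction" at f = 0.09.

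Neither paragraph names a deciding term, a month-6 contrast, a significance level or a multiplicity rule. The Exploratory aims paragraph, on the 18-month models, likewise looks for moderation through the group effect, the group-by-time term, or both.

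**The concern.** There are three linked problems.

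1. **No deciding test.** Two kinds of arm comparison serve one primary aim. With three visits, the interaction could be a linear term, a quadratic term or a joint 2-df test. If the deciding term is not fixed beforehand, the primary claim has no defined error rate.

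2. **The powered test does not match the aim.** The group effect is an average level over 21 days, 7 of them at baseline. It is not a difference in change.

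3. **The interpretation is wrong as a statement of inference.** A significant interaction says that the arm difference is not constant over time. It fixes neither the sign nor the shape. It could mean that A+P did worse, or that A+P gained at month 3 and lost the gain by month 6.

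At stake is the trial's main conclusion. A report could claim A+P superiority from a term that does not show a greater 0–6 month increase.

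**Working it through.** **Inputs.** From the Power paragraph: 57 per arm (N = 114), m = 21 measurements, r = 0.25, difference 10 min/d, SD 35 min/d (worded as the SD of change), f = 0.14 (10/35/2 = 0.1429). Assumption: two-sided alpha of 0.05. This reproduces the stated power, whereas 0.10 two-sided would give 87–88%.

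**1. The plan's own power.** For the between-groups test, λ = f²·N·m / [1 + (m − 1)r].
- f = 0.1429: λ = 0.02041 × 114 × 21 / 6 = 8.14; noncentral F(1, 112) gives 80.8%.
- f = 0.14: λ = 7.82; power 79.2%.

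The stated 81% is therefore the power of the group effect. For the interaction at f = 0.09, λ = 0.0081 × 2394 / 0.75 = 25.9 and F(20, 2240) gives 89%, consistent with at least 80%.

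The 81% needs an average difference of 10 min/d over all visits, baseline included. If the arms are equal at baseline and differ by 10 at months 3 and 6, the average is 6.67, λ = 8.14 × (2/3)² = 3.62, and the group effect has 47% power.

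**2. Error rates under no effect.** The group, linear and quadratic terms are treated as near-independent.

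| What counts as a positive result | Two tests | Three tests |
|---|---|---|
| Any term, either direction | 1 − 0.95² = 9.75% | 1 − 0.95³ = 14.3% |
| Group effect must favour A+P, any interaction counts | 1 − 0.975 × 0.95 = 7.4% | 1 − 0.975 × 0.95² = 12.0% |
| Every term must favour A+P | 1 − 0.975² = 4.9% | 1 − 0.975³ = 7.3% |

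Simulation of the first row (40,000 null trials, several covariance structures) gave 9.0–9.9% for the group effect plus one interaction test (linear or 2-df) and 13.2–14.4% for three. A single named two-sided test gives 5%.

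**3. A benefit gone by month 6.** Take true arm differences of 0, +10, 0 min/d at months 0, 3, 6. The quadratic contrast (−1, 2, −1) equals 20 and the linear contrast (−1, 0, 1) equals 0. Let u be the visit-level variance net of the between-visit covariance. Then SE(quadratic) = √(6u × 2/57).
- *35 is the SD of change:* u = 35²/2 = 612.5; SE = 11.36; 20/11.36 = 1.76.
- *35 is a single-day SD, r = 0.25 between all days:* u = 35² × 0.75/7 = 131.25; SE = 5.26; 20/5.26 = 3.80.

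| Term significant | SD of change 35 | Daily SD 35 |
|---|---|---|
| Quadratic | 42% | 97% |
| 2-df interaction | 33% | 93% |
| Linear interaction | about 5% | about 5% |
| Group effect | 14% | 16% |

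The mirror pattern (0, −10, 0), with A+P worse at month 3, gives essentially the same 2-df rates (32% and 93%).

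**4. Power of a single month-0-to-6 contrast for 10 min/d.**
- *SD of change 35:* SE = 35 × √(2/57) = 6.56; 10/6.56 = 1.53; power about 33%. About 193 per arm would be needed for 80%.
- *Daily SD 35, r = 0.25 throughout:* SD of change in weekly means = √(2 × 131.25) = 16.2; SE = 3.03; 10/3.03 = 3.30; power about 90%.
- *Daily SD 35, with an assumed within-week r of 0.50 and between-visit r of 0.25:* u = 35² × 4/7 − 0.25 × 35² = 393.75; SD of change = 28.1; SE = 5.26; power about 47%.

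**The case against.** The best defence is that the deciding term can be inferred. The aim is to compare changes, and the plan itself labels the interaction as the group difference in change. The sentence about significance is offered as an example and ends by describing a widening gap, so a gain lost by month 6 would contradict the plan's own gloss. The aim also expects the benefit in A+P, so an analyst would look at the estimates before claiming it.

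Part of this stands. The link between aim and interaction is there, and the fair charge is ambiguity rather than absence. But the Power paragraph rests the sample size on the group effect, and the form of the interaction is left open. The widening gap is asserted to follow from significance; nothing requires it to be checked.

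The objection also rules out three stronger readings that a reader might infer:

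- *The false-positive rate is 10–14%.* This needs two-sided 0.05 and any significant term in either direction to suffice, and the upper figure needs a separate quadratic test. The plan permits that reading but does not state it.
- *The plan counts a vanished benefit as success.* It does not say so. It fails to exclude it, and the route is a nonlinear or joint interaction, or at low rates the group effect.
- *The time form is chosen after seeing the data.* Fit criteria are applied only to the error covariance structure. The time form is unspecified, but no data-driven choice of it is described.

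**Conclusion.** The concern holds as an ambiguity in the primary test together with an incorrect interpretation sentence. It should be settled before analysis, because a term picked after results are known cannot be made confirmatory.

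Its size is conditional. The error inflation depends on the unstated alpha and on which terms and signs would count, and it disappears if one test is named. The exposure to a transient benefit depends on the interaction's form and on what the SD of 35 describes. The Power paragraph's wording (SD of change) gives the lower figures, and the visit-level covariance is not in the documents. Two conclusions need none of these assumptions: the group effect as defined does not test change, and a significant interaction alone does not establish that A+P increased more by month 6.

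**What to change.** In the Primary aim analysis paragraph:

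- Name one primary test: the A+P minus AO difference in change in MVPA from month 0 to month 6, from the mixed model with visit as a categorical factor, two-sided 0.05.
- Claim superiority only if the 95% confidence interval lies wholly above zero.
- Make the group effect, the month-3 difference and any trend terms supportive.
- Delete the sentence on what a significant interaction indicates, or correct it to say that the arm difference varies over time and that estimates and intervals at each visit must be read.

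In the Power paragraph, state alpha, say whether 35 min/d is the SD of each participant's change or of a single day, and restate power for the named contrast.

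A prespecified linear slope contrast would also control the error rate; categorical visit is preferred because it addresses the month-6 change directly. The error rate becomes 5%, and the transient pattern would be significant in only about 5% of trials.

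**Cost.** The edit is short, but it is more than wording. One route to significance is given up, and the 81% no longer applies. Power for 10 min/d at 57 per arm becomes about 33% if 35 is the SD of change as written, or about 90% if it is a single-day SD with r = 0.25 between all days, and lower if days within a week correlate more strongly. The sponsor would have to disclose whichever figure applies.

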
Primary aim: To compare changes in MVPA (min./d) between the AO and A+P groups across 6 mos. We expect a significantly greater increases in MVPA in adolescents in the A+P vs. the AO group.

Secondary aims: To compare changes between the AO and A+P groups on the following variables across 18 mos.: 1) MVPA (min/d) and sedentary time (adolescents and parents). Adolescents only: 2) cardiovascular fitness, 3) muscular strength, 4) motor ability, 5) quality of life. We will also compare the percentage of adolescents achieving an average of 60 min/d of MVPA (US recommendation) across 18 mos. We expect more favorable changes for all secondary outcomes in adolescents in the A+P vs. the AO group.

Exploratory aims. To examine the influence of the following process variables/participant characteristics to identify salient factors impacting change in MVPA across 18 mos.: attendance at group video (AO-adolescent; A+P-adolescent/parent) and education/support sessions (A+P only), self-monitoring of PA (AO-adolescent; A+P-adolescent/parent), parental use of Facebook page (A+P only), peer interactions/support during group PA sessions, adolescent self-efficacy, social support and barriers for PA, parental MVPA, parental beliefs and attitudes toward PA, and parental time constraints, adolescent age, sex and IDD diagnosis.

Rationale

Approximately 1-3% of the US population is diagnosed with an intellectual or developmental disability (IDD) defined as a disability originating before the age of 10, characterized by significant limitations in both intellectual functioning ($IQ < 75$) and limitations in 2 or more adaptive behaviors ¹. Both typically developing adolescents and adolescents with IDD have low levels of moderate-to-vigorous physical activity (MVPA) ^{2,3}. However, compared to their typically developing peers, adolescents with IDD have even lower daily MVPA ³. Phillips and Holland reported no adolescents with IDD achieved the recommended 60 min. of daily MVPA ⁴. In a previous trial by our group, MVPA, assessed by accelerometer of adolescents with IDD ($n=20$), was only 23 min./d ⁵. Low MVPA is associated with reduced cardiovascular fitness ^{6,7}, reduced muscular strength and endurance ^{8,9}, and high prevalence of overweight and obesity in adolescents with IDD ^{10,11}.

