Exploratory aims. If there are no between arm differences in the longitudinal change in MVPA across 18 mos., general mixed models will be fitted for the two arms combined to examine the association for the process variables/participant characteristics with MVPA. These variables include: attendance at group video (AO-adolescent; A+P-adolescent/parent) and education/support sessions (A+P only), self-monitoring of PA (AO-adolescent; A+P-adolescent/parent), parental use of Facebook page (A+P only), peer interactions/support during group PA sessions, adolescent self-efficacy, social support and barriers for PA, parental MVPA, beliefs and attitudes toward PA and parental time constraints, age, sex, and IDD diagnosis. However, if there is a significant group difference in MVPA, we will determine whether the previously listed process variables/participant characteristics explain/attenuate the intervention effect, i.e., moderation, by testing a 2-way interaction with the group effect and/or a 3-way interaction with the group-by-time interaction term. Some covariates will be measured only at baseline (age, sex, IDD diagnosis), some will be summarized across the trial (attendance at group video and education/support sessions, self-monitoring of PA, parental use of Facebook page, peer interactions/support during group PA sessions), while others will be assessed at specific time points (BMI, adolescent self-efficacy, social support and barriers for PA, parental MVPA, beliefs and attitudes toward PA and parental time constraints). Thus, we will carefully design our models to assure the appropriateness of the analysis. All analyses will be conducted using R and SAS 9.4 or higher.

Missing data. Missing due to either attrition, e.g., participant dropout or nonresponse, will be handled by multiple imputation, in which an expectation-maximization (EM) algorithm supplies prior estimates of missing values for a subsequent Monte Carlo Markov Chain (MCMC) procedure ⁶⁰. A sufficient number of imputed datasets will be created to ensure accurate recovery of missing data; and analysis results from each imputed dataset will be combined to make valid statistical inferences. All measured variables will be incorporated into the imputation process as auxiliary variables, thereby satisfying the missing at random (MAR) assumption ⁶¹.

REFERENCES

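### The exploratory aim asks which factors affect change in MVPA, but the pooled-arm analysis names only their association with MVPA, which is a test of level

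*Combined protocol and SAP*

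**What the plan says.** The Exploratory aims statement near the front of the protocol gives the purpose as "to identify salient factors impacting change in MVPA across 18 mos".

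The Exploratory aims paragraph under Analysis plan and statistical power has two branches.

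- **Pooled branch.** It opens "If there are no between arm differences in the longitudinal change in MVPA across 18 mos" and continues "general mixed models will be fitted for the two arms combined to examine the association for the process variables/participant characteristics with MVPA". No model term involving time is named.
- **Second branch.** If the arms do differ, the listed variables are examined as moderators "by testing a 2-way interaction with the group effect and/or a 3-way interaction with the group-by-time interaction term".

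The same paragraph distinguishes factors by when they are measured. Age, sex and diagnosis are taken at baseline; "some will be summarized across the trial (attendance at group video and education/support sessions, self-monitoring of PA, parental use of Facebook page", together with peer interaction; the rest, such as self-efficacy and parental MVPA, are measured at specific time points. It then gives a general assurance that the models will be designed with care.

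The Secondary Aim analysis paragraph gives the 18-month MVPA data as "7 days at each of 0, 3, 6, 9, 12, 15, and 18 mos. for MVPA and sedentary time". It also describes a related covariate analysis that will "assess their association with MVPA aggregated across months controlling for group".

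**The concern.** The aim is about change, while the pooled test as worded is about MVPA. The plan itself separates the two ideas. In the Primary aim analysis, a group effect is an overall difference across time, and a difference in change is carried by the interaction with time. By that usage, a factor effect without a time interaction is a level effect.

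Some adolescents are more active than others throughout. A factor that identifies them will be associated with MVPA even if it has nothing to do with who improves. The documents make such factors plausible. The Rationale cites cross-sectional studies linking greater parental support to higher activity, and the MVPA section scores adolescents under and over 18 by different rules, so age can relate to level partly through scoring.

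The pooled branch may well be the one used, because the Power paragraph says the secondary aims, which include the 18-month MVPA comparison, were not powered for arm differences. At stake is which factors the trial presents as relevant to increasing MVPA.

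**Working it through.** **The plan's own figure.** The documents compute nothing for the exploratory analysis. The nearest figure is 81% power for the group effect, from N = 114, m = 21 measurements, r = 0.25, a 10 min/d difference and an SD of 35 min/d (two-sided alpha 0.05 assumed).

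- f = (10/35)/2 = 0.1429.
- Noncentrality = f² × N × m / (1 + (m − 1)r) = 0.1429² × 114 × 21 / (1 + 20 × 0.25) = 8.14.
- Power on F(1, 112) = 80.8%. With f rounded to 0.14 it is 79.2%.

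The figure reproduces, so N and r are used below as the plan uses them. It does not bear on this point.

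**Setting.** 114 adolescents, 7 waves of 7 days (49 days), equal correlation r = 0.25 between any two days, and complete data. The factor has one value per adolescent, correlates rho with the adolescent's stable MVPA level, and has no relation to change. Values of rho are assumed. The SD does not affect these rejection rates.

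**Level test.** In balanced data the factor main effect is equivalent to correlating the factor with each adolescent's 49-day mean.

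- Share of the mean's variance that is stable level: 0.25 / (0.25 + 0.75/49) = 0.942; square root 0.971.
- Observed correlation = 0.971 × rho.
- Rejection rate from Fisher's z: Φ(z − 1.96) + Φ(−z − 1.96), with z = atanh(0.971 rho) × √111.

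| rho | z | Level test, formula | Level test, simulation | Change or slope test, simulation |
|---|---|---|---|---|
| 0 | 0 | 5% | 5–6% | about 5% |
| 0.1 | 1.03 | 18% | 17–18% | about 5% |
| 0.2 | 2.07 | 54% | 54–56% | 4–6% |
| 0.3 | 3.16 | 88% | 88–89% | 4–5% |
| 0.4 | 4.32 | 99% | 99% | 4–5% |

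With the pilot correlation, r = 0.22, the level test rejects in 18%, 55%, 88% and 99% for rho = 0.1 to 0.4.

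**Dropping month 0.** With 42 post-baseline days the multiplier is √(0.25 / (0.25 + 0.75/42)) = 0.966. At rho = 0.3, z = 3.14 and the rejection rate is 88%, essentially unchanged.

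**The reverse error.** Assume a factor that truly shifts change by 5 min/d per SD over 18 months, is unrelated to initial level, and has random slopes of SD 15 min/d (daily SD taken as 35). Simulation detects it in 29% of trials with the level test and 75% with factor-by-time.

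**Post-baseline MVPA adjusted for month-0 MVPA.** A 7-day month-0 mean measures stable level with reliability 0.25 / (0.25 + 0.75/7) = 0.70, so adjustment removes only part of the level association. Correlations: factor with post-baseline mean 0.966 rho; factor with month 0 √0.70 rho = 0.837 rho; post-baseline with month 0 0.966 × 0.837 = 0.808. The partial correlation is (0.966 − 0.837 × 0.808) rho / √((1 − 0.70 rho²)(1 − 0.808²)). At rho = 0.3 this is 0.087 / 0.570 = 0.153, z = atanh(0.153) × √110 = 1.61, and the rejection rate is about 36%. That is far below 88% but not 5%.

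**The case against.** The strongest reply is that this is one sentence about a hypothesis-generating aim, that it says association and claims no cause, and that the plan recognises that factors measured on different schedules need different models. The first two points limit the consequence. The third does not close the gap: the assurance concerns when covariates are measured, names no time term, and leaves the choice open until the data are in hand. Reading the pooled sentence as a main-effect test is an inference, but the natural one given the plan's own vocabulary.

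Several stronger readings are tempting, and the documents do not support them.

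- **That including month 0 is the cause.** The exploratory paragraph does not say which waves enter, and removing month 0 leaves the error rate almost unchanged. The missing time term is the problem.
- **That the 2-way interaction in the second branch is equally faulty and should be deleted.** Arms are randomised, so for a baseline factor the factor-by-group difference at month 0 is zero in expectation. In simulation that test rejected in about 5% of trials at every rho from 0 to 0.4. It can be less sensitive to moderation of change than the 3-way term, which is a matter of dilution and labelling.
- **That the percentages apply to every listed factor.** They hold for one value per adolescent. For self-efficacy, social support, barriers, parental MVPA, attitudes and time constraints, measured repeatedly, a single coefficient mixes within-person and between-person association, and stable level does not drive the within-person part.
- **That level markers will certainly be reported as drivers of change.** That requires a factor that correlates with level, and the documents give no such correlation.

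**Conclusion.** The mismatch between aim and analysis stands. As written, the pooled branch answers which factors go with higher MVPA, and it can miss factors that go with change. For a time-invariant or trial-summarised factor unrelated to change, the false-positive rate is about 17%, 55%, 89% and 99% at correlations of 0.1, 0.2, 0.3 and 0.4 with stable level, against about 5% for a test on change.

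This rests on the plan's N and r, an equal-correlation structure, complete data, two-sided alpha of 0.05, and an assumed range for the factor's correlation with level. A reader might infer that the trial's main findings are compromised. They are not: only exploratory conclusions are affected, and the primary and secondary comparisons are untouched. The point deserves correction because the remedy needs no new data.

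**What to change.** In the Exploratory aims paragraph of the analysis plan:

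1. **Pooled branch, time-invariant and trial-summarised factors.** Make the factor-by-time term the test of the aim, with month 0 as reference, and report each factor's association with change from month 0. Keep group and group-by-time in the model. Post-baseline MVPA adjusted for month-0 MVPA is an alternative and much better than the level test. Because month 0 is a noisy measure of level, it does not hold the error at 5%, so it is better used as support than as the deciding test.
2. **Factors measured repeatedly.** Separate the within-person from the between-person association. A factor-by-time term alone would ask only whether the association varies over time.
3. **Labelling.** Describe any factor main effect as association with MVPA level.
4. **Second branch.** The 2-way interaction may stay, but moderation of change should be read from the 3-way term.

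The cost is wording and one more interaction term per model. Factors related only to level will no longer count as findings.
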